5.2.2 Study flow charts

122 people were recruited and informed consent was signed. Diagnosis was made according to imaging, and subjects were screened according to inclusion and exclusion criteria.

The medical history, imaging data and test results of the subjects were collected. Baseline assessment was performed to determine whether subjects tolerated general anesthesia surgery.

The lower alveolar nerve function was detected before operation: light touch detection, acupuncture detection, hot and cold stimulation, two-point discrimination detection.

Surgical treatment

Lower alveolar nerve function was detected 1 month after operation: light touch detection, acupuncture detection, hot and cold stimulation, two-point discrimination detection.

The main study measure: postoperative nerve injury rate was calculated until the last subject was followed up.

5.2.3 Research schedule

Interview	Screening period	Before operation	Operation	Follow-up visit			
	V1	V2	V3	V4	V5	V6	V7
Follow-up time	1 day before enrollment	Enrollment day	Day after V2	1 week after surgery	One month after surgery	Three months after surgery	1 year after surgery
Sign informed consent	✓						
Inclusion/exclusion criteria	✓						
Demographic data	✓						
Medical history	✓						
Neural test score		✓			✓		
Physical examination	✓	✓	✓	✓	✓	✓	✓
Vital sign	✓	✓	✓	✓	✓	✓	✓
Electrocardiogram	✓						
Blood routine examination	✓						
Blood biochemistry	✓						
Liver function	✓						
Coagulation function	✓						
Imaging examination	✓				✓		✓
Pathological examination			✓				
Epidemiological examination	✓						
Adverse event evaluation			✓	✓	✓	✓	✓

5.3 Definition of study end

The end of the study was defined as the last subject to complete the last follow-up or loss of follow-up or death.

5.4 Statistical Analysis

5.4.1 Sample size and calculation basis

The main efficacy index of this study was the postoperative nerve injury rate of endoscopic combined with intraoperative navigation-assisted treatment of giant mandibular bone cysts. The hypothesis of this study is that the postoperative nerve injury rate of endoscopy combined with intraoperative navigation-assisted treatment of giant mandibular cyst is lower than that of traditional excision and curettage. Research parameters were set as follows: $\alpha=0.025$ (unilateral) and Power=80%. According to the results of previous studies or pre-trials, the postoperative nerve injury rate in the endoscopic navigation group was reduced by about 20% to 12%. 109 cases were calculated using PASS 15.0 software, and 122 subjects were included considering the 10% shedding rate.

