2.1 Research theoretical basis/background

Odontogenic jaw cyst is a unique disease affecting the mouth and mandible. Its occurrence is closely related to the development and formation of dental tissue and inflammation. The four most common odontogenic jaw cysts include periapical cyst, odontogenic cyst, residual cyst, and odontogenic keratosis cyst¹. Most cysts grow slowly and may have only mild or no symptoms. When cysts grow larger, they can damage the surrounding tissue, leading to maxillofacial swelling, infection, root resorption, nerve damage, pathological fracture, and even malocclusion². Smaller odontogenic jaw cysts can be removed directly by surgery, while the treatment of larger odontogenic jaw cysts remains controversial. Some scholars believe that fenestration decompression is an effective and conservative treatment³, but some scholars believe that although fenestration decompression is less traumatic, patients will be accompanied by discomfort during the long healing period, and direct surgery to remove the complete lesion is the best choice⁴.

In a previous retrospective study of 25 patients with large mandibular cysts who underwent traditional removal and curettage surgery, 8 patients developed symptoms of nerve damage after surgery, with a postoperative nerve damage rate of up to 32%.

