5.1 Overall Design

This study hypothesized that endoscopy combined with intraoperative navigation-assisted treatment of giant mandibular bone cysts was more effective than the traditional surgical method of removal and curettage. In this study, a prospective, single-arm, Phase II clinical study was used to design the protocol, and the estimated rate of postoperative nerve injury was reduced by about 12% from 32% to 20% compared with traditional surgery.

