5.4.2 Data Analysis Set

Statistical analysis will be performed using SAS statistical analysis software (V.9.4, SAS Institute). If there is no special explanation, unilateral test will be used for the main index, and the control error α is 0.025; bilateral test will be used for the other indicators, and the error α is =0.05. If you need to calculate confidence intervals, calculate bilateral 95% confidence intervals unless otherwise specified.

- (1) full analysis set (FAS) : comprised of all subjects who underwent surgical treatment and were evaluated for efficacy. The data set is derived from all subjects by eliminating subjects in a minimal and reasonable way.
- (2) safety analysis set (SS) : A group of people who have received surgical treatment and have safety evaluation data. In the safety analysis, all patients will be analyzed according to the actual surgical group received.
- (3) per-protocol set (PPS) : all subjects who met the protocol and did not use concomitant drugs that affected the effectiveness evaluation, had good medication compliance (between 80% and 120%), and excluded subjects who had a major protocol violation and were judged to have a significant impact on the results. All trial protocol deviations that result in subjects being excluded from the conformance protocol set will be detailed in the Statistical Analysis Plan (SAP) and completed prior to data locking.

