5.4.3 Statistical Analysis Plan

Data description of statistical analysis, analysis methods of primary/secondary indicators/safety indicators, statistical correction methods, bias control, stratification/subgroup/sensitivity analysis, etc.

Demographic and other baseline characteristics: Based on FAS set, demographic data, medical history, vital signs and other baseline data were statistically described. The mean, standard deviation, minimum, maximum and median values were given for measurement data (age, BMI, body weight, blood pressure, etc.). Counting data (gender, tobacco and alcohol history, etc.) give the frequency and corresponding percentage.

Analysis of efficacy index: The main evaluation index (postoperative nerve injury rate) was estimated by point and the bilateral 95% confidence interval was estimated by Clopper-Pearson exact probability method. If the lower limit of the 97.5%

confidence interval is lower than the postoperative nerve injury rate of the historical control, it is considered that the efficacy of the navigational endoscopy group is better than the historical control. Secondary efficacy indicators were analyzed using FAS and PPS analysis sets. For postoperative recurrence indicators, the median postoperative recurrence time and bilateral 95% confidence interval were calculated. For the rates of each index, point estimation was performed and the Clopper-Pearson accurate probability method was used to estimate the bilateral 95% confidence interval. For the continuity index, if it conforms to the normal distribution, its mean and bilateral 95% confidence interval are calculated based on the normal distribution method, otherwise based on hundreds. The quantile method calculates the median and bilateral 95% confidence intervals.

Analysis of safety indicators: SS sets were used to make statistical descriptions of the incidence of adverse events/serious adverse events, adverse reactions and other safety indicators, and to list and describe the details of each adverse event for each subject, including the type and severity of adverse events. Laboratory indicators, vital signs, electrocardiogram and other safety-related indicators were compared and evaluated before and after treatment, and clinical evaluation (normal, abnormal no clinical significance, abnormal clinical significance, no investigation) was given before and after treatment for statistical description.

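### Section 5.4.1 states the wrong planning rates: 109 and 122 follow from 32% to 20% (Section 5.1), not from the 20% and 12% written there

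*Protocol*

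**What the plan says.** Protocol Section 5.4.1 sets a one-sided alpha of 0.025 and 80% power. Its hypothesis is that the injury rate after the navigated endoscopic procedure for "giant mandibular cyst is lower than that of traditional excision and curettage". It then gives the planning rates, saying that "the postoperative nerve injury rate in the endoscopic navigation group was reduced by about 20% to 12" percent, and the result: "109 cases were calculated using PASS 15.0 software, and 122 subjects were included considering the 10% shedding rate". It does not state a rate for the comparator.

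Section 5.1, describing the same single-arm design and endpoint, says that "the estimated rate of postoperative nerve injury was reduced by about 12% from 32% to 20% compared with traditional surgery". Section 2.1 gives the source of the 32%: a retrospective series in which 8 of 25 patients had nerve damage after traditional surgery, "with a postoperative nerve damage rate of up to 32" percent.

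Section 5.4.3 compares a confidence limit with the control and asks whether it is "lower than the postoperative nerve injury rate of the historical control". It does not give the value of that rate.

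**The concern.** Sections 5.1 and 5.4.1 give different rates for one calculation. Section 5.4.1 is the formal sample-size statement, and its alpha, power, rates and sample size do not fit together as written. A reader working from that section alone could conclude that the trial is badly underpowered or about three times too large, depending on how the phrase is read.

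The planning rate for the comparator is also the value against which success is judged. Section 5.4.3 leaves that value unnumbered, and the first rate printed in Section 5.4.1 is 20%. A reader could therefore take 20% as the benchmark in place of 32%, and some results would then change verdict.

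**Working it through.** **Inputs**

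- Alpha: 0.025 one-sided (Section 5.4.1; Section 5.4.2 repeats that a "unilateral test will be used for the main index, and the control error α is 0.025"). z = 1.960.
- Power: 80% (Section 5.4.1). z = 0.8416.
- Design: single arm against a fixed historical rate (Sections 5.1 and 5.4.3).
- Control rate: 8/25 = 32% (Section 2.1).
- Stated result: 109 evaluable, 122 with 10% dropout (Section 5.4.1).

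**Formula** (one-sample proportion, normal approximation)

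n = [(1.960 × √(p0(1−p0)) + 0.8416 × √(p1(1−p1))) / (p0 − p1)]²

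**Step 1. Reproduce the plan's figure with the rates of Section 5.1 (32% to 20%).**

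- √(0.32 × 0.68) = 0.4665 and √(0.20 × 0.80) = 0.4000.
- Numerator: 0.9143 + 0.3366 = 1.2509.
- n = (1.2509 / 0.12)² = 108.67, rounded up to 109.
- Dropout: 109 / 0.9 = 121.1, rounded up to 122.

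Both stated figures are reproduced. An exact binomial search also gives 109 as the smallest n reaching 80% power. Success is at most 25 injuries, with actual alpha 0.0246 and power 81.4%.

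**Step 2. Try each reading of the sentence in Section 5.4.1.**

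(a) A fall from 20% to 12%. √(0.12 × 0.88) = 0.3250, so the numerator is 0.7840 + 0.2735 = 1.0575 and n = (1.0575 / 0.08)² = 174.7, rounded up to 175.

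(b) A fall of 20 points, from 32% to 12%. The numerator is 0.9143 + 0.2735 = 1.1878 and n = (1.1878 / 0.20)² = 35.3, rounded up to 36.

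(c) A range of reductions of 12 to 20 points from 32%. This gives 109 only at the 12-point end, which is again 32% to 20%.

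| Rates | n, normal | smallest exact n | exact power at 109 |
|---|---|---|---|
| 32% to 20% | 109 | 109 | 81.4% |
| 20% to 12% | 175 | 173 | 56.4% |
| 32% to 12% | 36 | 33 | 99.96% |

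**Step 3. Could another formula turn 20% to 12% into 109?** At one-sided 0.025 the variants give:

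- continuity correction: 187
- arcsine: 163
- variance at p1 only: 130
- variance at p0 only: 197
- two-sample comparison: 329 per arm

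At one-sided 0.05 the standard formula gives 136, and the p1-only variance gives 102, or 115 with continuity correction. None gives 109.

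**Step 4. What the benchmark does to the verdict.** With 109 evaluable patients and an exact one-sided 0.025 test pointing in the right direction, success needs at most 25 injuries if the benchmark is 32%, and at most 13 (actual alpha 0.0189) if it is 20%. Results of 14 to 25 injuries change verdict with the benchmark. The count expected at the planned 20% rate is 109 × 0.20 = 21.8, inside that zone.

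**The case against.** The strongest case on the other side is that nothing of substance changes. The right rates are already printed in Section 5.1 and their source in Section 2.1. The sentence in Section 5.4.1 looks like two transposed figures (a fall of 12 points, to 20%), and 32% is the only rate the protocol gives for traditional surgery, so a reader of the whole document can recover both the calculation and the benchmark. A SAP that is not shown may restate the number. On this view the point is a clarification.

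Most of that is fair as to cause, and it is why the sample size is not challenged here. It does not remove the need to correct. The section that formally justifies the sample size is wrong as written, and the benchmark should not have to be inferred.

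Three limits on the claim also stand.

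- The rates 32% and 20% are the only pair giving 109 among those the protocol states. Unstated neighbours, such as 31% to 19%, 33% to 21% and 26% to 15%, also have a smallest exact n of 109.
- The check shows that 109 is consistent with Section 5.1. It does not validate a 32% benchmark taken from 25 patients.
- The 175 for 20% to 12% is a normal-approximation figure. Exact power is 79.5% at 175. It reaches 80% at 173 and 174, falls below it from 175 to 178, and is above it again at 179.

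**Conclusion.** The concern holds. Sections 5.1 and 5.4.1 contradict each other, and the arithmetic shows that the misstatement is in Section 5.4.1: 109 and 122 follow exactly from 32% to 20% and from no reading of 20% and 12%. On the rates of Section 5.1 the trial has 81.4% exact power at 109 evaluable patients. The 56.4% applies only if 20% to 12% was truly intended, and nothing else in the protocol supports that.

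The conclusion assumes a one-sample test against a fixed rate at one-sided 0.025, as the protocol describes. The correction should be made before data are seen, because the same number sets the bar for success. The use of the lower confidence limit in the Section 5.4.3 decision rule is a separate error, which this correction does not cure.

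**What to change.** In Section 5.4.1, replace the sentence on rates with: historical control rate p0 = 32%, expected rate p1 = 20% (absolute reduction of 12 percentage points), one-sample test of a proportion, one-sided alpha 0.025, power 80%; 109 evaluable patients, 122 with 10% dropout. In Section 5.4.3, give 32% as the value of the historical control.

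The sponsor should confirm that 32% to 20% was intended. If so, the cost is one sentence and one number, and sample size, alpha and power are unchanged.

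If 20% to 12% was intended, either restate the power at 109 as about 56%, or raise the sample size to about 175 evaluable (175 / 0.9 = 194.4, so 195 enrolled). In that case settle the final figure by exact calculation, since the analysis uses Clopper-Pearson limits and exact power is slightly under 80% at 175 itself.

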5.4.2 Data Analysis Set

Statistical analysis will be performed using SAS statistical analysis software (V.9.4, SAS Institute). If there is no special explanation, unilateral test will be used for the main index, and the control error α is 0.025; bilateral test will be used for the other indicators, and the error α is =0.05. If you need to calculate confidence intervals, calculate bilateral 95% confidence intervals unless otherwise specified.

- (1) full analysis set (FAS) : comprised of all subjects who underwent surgical treatment and were evaluated for efficacy. The data set is derived from all subjects by eliminating subjects in a minimal and reasonable way.
- (2) safety analysis set (SS) : A group of people who have received surgical treatment and have safety evaluation data. In the safety analysis, all patients will be analyzed according to the actual surgical group received.
- (3) per-protocol set (PPS) : all subjects who met the protocol and did not use concomitant drugs that affected the effectiveness evaluation, had good medication compliance (between 80% and 120%), and excluded subjects who had a major protocol violation and were judged to have a significant impact on the results. All trial protocol deviations that result in subjects being excluded from the conformance protocol set will be detailed in the Statistical Analysis Plan (SAP) and completed prior to data locking.

5.4.3 Statistical Analysis Plan

Data description of statistical analysis, analysis methods of primary/secondary indicators/safety indicators, statistical correction methods, bias control, stratification/subgroup/sensitivity analysis, etc.

Demographic and other baseline characteristics: Based on FAS set, demographic data, medical history, vital signs and other baseline data were statistically described. The mean, standard deviation, minimum, maximum and median values were given for measurement data (age, BMI, body weight, blood pressure, etc.). Counting data (gender, tobacco and alcohol history, etc.) give the frequency and corresponding percentage.

Analysis of efficacy index: The main evaluation index (postoperative nerve injury rate) was estimated by point and the bilateral 95% confidence interval was estimated by Clopper-Pearson exact probability method. If the lower limit of the 97.5%

confidence interval is lower than the postoperative nerve injury rate of the historical control, it is considered that the efficacy of the navigational endoscopy group is better than the historical control. Secondary efficacy indicators were analyzed using FAS and PPS analysis sets. For postoperative recurrence indicators, the median postoperative recurrence time and bilateral 95% confidence interval were calculated. For the rates of each index, point estimation was performed and the Clopper-Pearson accurate probability method was used to estimate the bilateral 95% confidence interval. For the continuity index, if it conforms to the normal distribution, its mean and bilateral 95% confidence interval are calculated based on the normal distribution method, otherwise based on hundreds. The quantile method calculates the median and bilateral 95% confidence intervals.

Analysis of safety indicators: SS sets were used to make statistical descriptions of the incidence of adverse events/serious adverse events, adverse reactions and other safety indicators, and to list and describe the details of each adverse event for each subject, including the type and severity of adverse events. Laboratory indicators, vital signs, electrocardiogram and other safety-related indicators were compared and evaluated before and after treatment, and clinical evaluation (normal, abnormal no clinical significance, abnormal clinical significance, no investigation) was given before and after treatment for statistical description.

The processing principle of missing/deleted/lost data: LOCF (last observation carried forward) method was adopted to fill in the analysis of main indicators, that is, the last observed data was used to fill in the data that failed to observe the main indicators. Secondary indicators and security indicators are not filled.

VI. Research and intervention

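### The primary success rule tests the wrong end of the confidence interval, so a surgery no better than the historical control would be declared superior about 98% of the time

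*Protocol*

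**What the plan says.** Protocol 5.4.1 sets the direction: "The hypothesis of this study is that the postoperative nerve injury rate of endoscopy combined with intraoperative navigation-assisted treatment of giant mandibular cyst is lower". The comparator is traditional surgery. The section gives a one-sided alpha of 0.025, 80% power, 109 evaluable patients and 122 enrolled. Protocol 5.4.2 repeats the error rate: "unilateral test will be used for the main index, and the control error α is 0.025".

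Protocol 5.4.3 gives the analysis. The rate is estimated with an exact interval: "the bilateral 95% confidence interval was estimated by Clopper-Pearson exact probability method". The decision sentence follows. It begins "If the lower limit of the 97.5"% and its second half starts "confidence interval is lower than the postoperative nerve injury rate of the historical control, it is considered that the efficacy of the navigational endoscopy group". The conclusion drawn there is superiority over the historical control.

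That sentence gives no number for the historical rate. The figure comes from Protocol 2.1, where in a retrospective series of 25 patients "8 patients developed symptoms of nerve damage after surgery, with a postoperative nerve damage rate of up to 32"%, and from Protocol 5.1, which plans a fall from 32% to 20%. No other section of the protocol states a success rule based on the upper limit.

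**The concern.** To show that a rate lies below a reference, the whole interval must lie below it, so its upper limit is the one to compare. A lower limit below the reference is met by every result except one significantly worse than the control. The sentence therefore labels a failure to show harm as proof of benefit.

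This is the only explicit success sentence for the primary endpoint. Followed literally, it cannot hold the one-sided 0.025 that 5.4.1 and 5.4.2 promise, and meeting it would carry no evidence of benefit.

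A smaller point sits in the same sentence. The interval estimated is a two-sided 95% one, but the decision refers to a 97.5% interval without saying whether that is one-sided or two-sided.

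**Working it through.** **Inputs.** Historical rate p0 = 0.32 (Protocol 2.1, 8/25; Protocol 5.1). Expected rate p1 = 0.20 (5.1). One-sided alpha 0.025, power 80%, n = 109 evaluable and 122 enrolled (5.4.1). Clopper-Pearson limits (5.4.3).

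**Step 1: reproduce the stated sample size.** For a one-sample, one-sided test,

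n = [(z₀.₉₇₅·√(p0(1−p0)) + z₀.₈₀·√(p1(1−p1))) / (p0−p1)]²

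= [(1.960 × 0.4665 + 0.8416 × 0.4000) / 0.12]² = (1.2509 / 0.12)² = 108.7, rounded up to 109.

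With 10% dropout, 109 / 0.90 = 121.1, rounded up to 122. Both stated figures are reproduced. Section 5.4.1 words the effect as 20% and 12%. Reading those as the two rates gives 175, not 109, so 32% against 20% is the design behind the stated number.

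**Step 2: the rule as written.** For x injuries in n patients,

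- lower limit L(x) = 0.025 quantile of Beta(x, n−x+1)
- upper limit U(x) = 0.975 quantile of Beta(x+1, n−x)

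The largest x with L(x) < 0.32 is:

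- n = 109: x = 45 (41.3%), lower limit 31.9%
- n = 122: x = 49 (40.2%), lower limit 31.4%

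An observed rate 9.3 points (41.3 − 32) or 8.2 points (40.2 − 32) above the control would still be declared better.

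The probability of declaring superiority is the binomial P(X ≤ 45) or P(X ≤ 49):

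| True injury rate | n = 109 | n = 122 |
|---|---|---|
| 32% (no better) | 98.4% | 97.7% |
| 35% | 92.9% | 90.1% |
| 40% | 64.7% | 55.4% |
| 45% | 24.8% | 16.3% |
| 50% | 4.2% | 1.8% |

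**Step 3: the upper-limit rule.** The largest x with U(x) < 0.32 is:

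- n = 109: x = 25 (22.9%), upper limit 31.97%; type I error P(X ≤ 25 given 0.32) = 2.46%; power P(X ≤ 25 given 0.20) = 81.4%
- n = 122: x = 28 (23.0%), upper limit 31.4%; type I error 1.83%; power 82.4%

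These match the stated alpha and power.

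**Step 4: sensitivity to the 97.5% label.** Each limit of a two-sided 95% interval is a one-sided 97.5% limit, so a one-sided reading changes nothing above. On a two-sided 97.5% reading (0.0125 in each tail):

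- lower-limit rule as written: up to 46/109, success at a true 32% in 99.0%
- upper-limit rule: at most 23/109, type I error 0.81%, power 66.5%; or at most 27/122, type I error 1.08%, power 76.2%

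**Step 5: sensitivity to the reference rate.** If the reference were 20%, the rule as written would pass up to 30/109 (27.5%) and succeed with probability 97.8% at a true rate of 20%. The defect does not depend on the choice of 32%.

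**The case against.** The strongest reply is that this is a slip of wording, perhaps of translation, and not of design. Sections 5.4.1 and 5.4.2 name a one-sided test at 0.025 in the right direction, and the sample size reproduces for exactly that test. The reported interval would also show any reader its upper limit. All of this is fair, and it makes the intended rule clear. It does not repair the text. Sections 5.4.1 and 5.4.2 give no decision sentence, 5.4.3 contradicts them, and the written rule governs until it is amended. A change made after the results are known would look post hoc.

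The reply is also right that the rule does not pass everything. A surgery with a true rate of 45% or 50% would usually fail it. The near-certain false success applies to a surgery no better or slightly worse than the control.

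The 97.5% label, taken alone, is a matter of clarity. Its natural reading, a one-sided 97.5% bound, agrees with alpha 0.025.

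Finally, 32% has to be inferred, because the decision sentence gives no number and 5.4.1 is worded differently from 5.1. The reproduction of 109 supports 32%, and the defect remains at 20%.

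**Conclusion.** The concern holds, and the sentence must be corrected before the analysis. As written, the rule has a false-positive probability of about 98% at no benefit (98.4% with 109 patients, 97.7% with 122), against the stated 2.5%. It would also call an observed injury rate of about 40% to 41% better than 32%. These figures assume a fixed historical rate of 32%, exact Clopper-Pearson limits at 0.025 in each tail, and 109 or 122 patients analysed. Reading 97.5% as two-sided, or taking 20% as the reference, leaves the conclusion unchanged.

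**What to change.** Replace the decision sentence in Protocol 5.4.3 with wording such as: *If the upper limit of the two-sided 95% Clopper-Pearson confidence interval (equivalently, the one-sided 97.5% upper bound) is below 32%, the nerve injury rate is considered lower than the historical control rate.* Delete the separate reference to a 97.5% interval. Because the new sentence names 32%, bring the effect stated in 5.4.1 into line with 5.1 in the same amendment.

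The cost is one sentence in 5.4.3 and a matching correction in 5.4.1, submitted to the ethics committee as the protocol's section on ethical requirements already provides. The sample size stays as it is, and no additional patients or data are needed.
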